The outcome measures will be surgeon-specific and patient-specific. These outcome measures for the 'Trainee' group will commence following completion of the simulation training (if applicable), whereas they can commence immediately following study approval for the 'Expert' group. The surgeon-specific outcome measures will be the objective motion-analysis metrics generated by validated and extensively used wireless sensors placed on the elbows of surgeons under their sterile gowns during the operation; and subjective assessments of surgical trainee performance using validated and reliable forms of structured human grading. Patient-specific outcome measures will be collected for a pre-determined number of patients who have undergone a primary elective THR by any of the surgeon participants in this study. All patient-specific outcome measures (with the exception of a post-operative questionnaire) are routinely collected as part of the patients NHS clinical care, and no other additional investigations are required for conducting this research. All patients will be asked to provide their written informed consent for the use of their data in this study. The patient-specific outcome measures include: pre- and post-operative blood tests and radiograph (X-ray) analysis; the incidence of blood transfusions and any other peri-operative complications; the in-patient length of stay; and two patient-reported outcome measure (PROMs) questionnaires.

Statistical analysis will then be performed on the data collected, specifically aiming to identify any significant differences in either surgeon performance metrics, or patient outcome measures between:

- 1) The StR's who have undertaken additional simulation training versus those who have routine Deanery training.
- 2) The 'Trainee' group and the 'Expert' group. A sub-group analysis may be performed within the 'Expert' group also to determine any differences between the Consultants and Fellows.

In summary, this novel research will use validated methodology and routinely collected patient outcome measures in order to determine the impact of simulation training on surgical trainee performance and patient outcomes following a primary elective THR, and also help to benchmark an expert level of performance in this commonly performed and highly effective operation. The results of this study will hopefully help in shaping the future of orthopaedic surgical training and assessment within the United Kingdom.

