9.7 Intra-operative surgeon performance data collection

The following protocol will apply to all episodes of intra-operative performance data collection for StR's and Fellows. The intra-operative data collection for Consultant performed operations will differ slightly in that they require no supervision, and no surgeon will 'take over' the operation. However, the methods for recording the intra-operative data will remain the same.

A maximum of two study participants (excluding Consultants) will attend any given list. The PI ([name]) will attend the World Health Organisation (WHO) briefing in theatre on the morning of the list, introduce themselves and explain their role during the list. If recording an StR, neither the participant or PI will disclose which arm of the study the participants are in (routine training, or additional simulation training). The supervising Consultant will confirm the cases on the list the StR or AF's will be performing under supervision and training.

Operative protocol

After anaesthesia and patient set-up, the supervising Consultant and participant will scrub in up in the usual manner with the motion sensors in position on the lead surgeon's elbows under their sterile gown (see Appendix C). The procedure will then continue routinely and normally, but with the PI collecting motion data via the wireless Bluetooth sensors. The PI will also manually record the timings of each stage of the THR operation. This process will allow synchronisation of motion data to the participants progression throughout the stages of the operation. Data collection will stop when the dressing has been applied to the surgical wound.

Following completion of the operation, the participants in conjunction with the supervising Consultant will be asked to complete short written assessments of the lead surgeons' intra-operative performance. These assessments may include: Global Rating Scales (GRS), Objective Structured Assessment of Technical Skills (OSATS), and surgical checklists.

Intra-operative deviations or interruptions

Sometimes the supervising Consultant needs to take over part or all of an operation if it proves particularly difficult. In the event that a procedure has to be taken over completely by the Consultant then data recording will stop. If minor adjustments only are made by the Consultant during the operation then these will be noted and time marked against the motion data.

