11 STATISTICS AND ANALYSIS

Analysis of motion data.

Motion data from the wireless sensors produces performance surrogate markers such as: the number of movements (major & minor); total path length; and smoothness/economy of movement. Data distributions will be assessed for normality using the Shapiro-Wilk test. Previous studies show such data are not normally distributed, and we would expect to use non-parametric tests, such as the Mann-Whitney U test to compare the performance metrics between the 2 groups of participants (StR's against Experts & Fellows). The Mann-Whitney U test will also be used to compare performance metrics between the two sub-groups of StR's (control and intervention), and also within the intervention sub-group in order to compare performance before and after training.

Performance metrics within all groups of participants will be reported using descriptive statistics to outline the central tendency (mean, median, and mode) and variation (range, variance, and standard deviation) in readings obtained. The Kruskal-Wallis one-way analysis of variance (ANOVA) test will be used to test for differences in the mean values obtained for all performance metrics between the two groups of participants. The Wilcoxon signed-rank test will be used to determine any differences in performance metric between the two groups.

Analysis of other routinely obtained data

X-ray (radiograph) analysis:

X-rays will be reviewed by two independent Consultant Orthopaedic Surgeons who will be blinded to the patient and lead surgeon's identity in order to reduce bias. There are several important parameters to be evaluated when reviewing a pelvic x-ray, therefore we will ask each reviewer to allocate a categorical global rating (see below) for both the pre- and post-operative x-rays. [5] The Chi-squared test will be used

to determine if there are any significant differences between each group, and also intra-group differences (for example StR's before and after additional training).

Pre-operative x-ray

- 1: Hip osteoarthritis without significant bone loss.
- 2a: Hip osteoarthritis with significant bone loss on acetabular side.
- 2b: Hip osteoarthritis with significant bone loss on femoral side.
- 3: Hip osteoarthritis with significant bone loss on both acetabular and femoral sides.

Post-operative x-ray

- 1: Excellent implant position and restoration of hip anatomy.
- 2a): Good overall with minor imperfections on acetabular side.

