- 2b): Good overall with minor imperfections on femoral side.
- 3: Moderate concerns but does not require revision surgery.
- 4: Significant concerns requiring revision surgery.

Every patients post-operative x-ray will also be reviewed by the PI ([name]) for acetabular component positioning (inclination and version) using the methodology described by Bachhal [4]. This continuous data will be assessed for normality of distribution, and analysed using similar methodology as described above for the motion data. We will be looking for any statistically significant differences between the 2 groups of participants, within the two sub-groups of StR's (control and intervention), and also within the intervention sub-group in order to compare performance before and after additional training.

Other outcomes data:

Following collection of the outcome measures listed below, the normality of the data distribution will be checked with the Shapiro-Wilk test. Descriptive statistics will be used to outline the central tendency and variation of these data sets. Statistical analyses between each group of participants will be performed using either the parametric unpaired t-test or a non-parametric Mann-Whitney U test depending on the distribution of the data. Subsequent analysis of the outcomes data using a paired t-test, or Mann-Whitney U test will also be performed within the two sub-groups of the StR's (control and intervention), and also within the intervention sub-group in order to compare outcomes before and after additional training.

- Theatre time usage.
- Blood loss (pre-/post-op haemoglobin levels)
- In-patient length of stay.
- PROMs: EQ-5D and OHS.

The Chi-squared test (or Fishers exact test if the sample is <5) will be used to determine any significant differences between the groups regarding the incidence of blood transfusions or peri-operative morbidity.

All of these tests will be performed using the SPSS statistical package, which is available for any registered student on the University of Oxford current Licencing agreement.

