12 DATA MANAGEMENT

Within this study both patients and participants will have all of their personal data anonymised via the use of Unique Patient or Participant Identifiers (UPI's). A master list of key linking identifiers for both patients

and participants will be kept on a password protected file on the OUH secure Trust Network Server. Only completely anonymised data will be used outside of OUH Trust property, which will be kept on a password-protected University owned laptop or hard-drive. We plan on keeping study data for a period of 5 years following completion on the study (up to December 2026), before securely disposing of it. We believe that this storage is appropriate as the core content is scientific research data and is therefore in the public interest. Furthermore, we will require access to this data in the case of individuals wishing to scrutinise the scientific methodology, results, or conclusions of our study.

Intra-Operative Data

Raw data will be produced from the wireless sensors. Please see section 12.3 for further details regarding the recording, transfer, and storage of this data.

Other 'personal data'

1) Electronic Patient Record Data

The following data will be obtained from the NHS Electronic Patient Records (EPR), which includes the Insignia Picture Archiving and Communication System (PACS), and the Theatre Management System (TMS):

- X-ray (radiograph) analysis.
- Theatre time usage.
- Blood test & transfusion rate analysis.
- Peri-operative morbidity (30 day).
- In-patient length of stay.
- Patient demographics (age, gender, BMI)

2) Questionnaire Data

Patient Questionnaire Data

The patient questionnaires consist of the following components:

- Patient Reported Outcome Measures: The OHS and EQ-5D.

Participant (Medical Health Professionals) Questionnaire Data

Written assessments of intra-operative performance will be conducted shortly after completion of a recorded THR. These assessments may include: Global Rating Scales (GRS), Objective Structured Assessment of Technical Skills (OSATS), and surgical checklists. The data collected from these will be anonymised as it will be linked with the UPI, and not provide any names or other personal information. The hard copies will be transcribed into digital format as soon as possible, which will be stored onto a password protected encrypted file on a University owned computer/hard-drive. The hard copies of the forms will then be disposed of.

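### Patient age, sex and BMI are collected but enter no analysis, so theatre time, motion metrics and length of stay are compared unadjusted, with a modest and avoidable loss of precision

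*Combined protocol and SAP*

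**What the plan says.** Section 12 (Data Management, electronic patient record data) lists "Patient demographics (age, gender, BMI") among the items to be extracted, and the schedule in Appendix B includes demographics.

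Section 11 is the whole analysis plan.
- Motion data: "The Mann-Whitney U test will also be used to compare performance metrics between the two sub-groups of StR's (control and intervention"), and the same test is expected for StRs against Experts and Fellows.
- Other outcomes, which include "Theatre time usage" and "In-patient length of stay": "Statistical analyses between each group of participants will be performed using either the parametric unpaired t-test or a non-parametric Mann-Whitney U test". The choice follows a normality check.
- The remaining methods are Shapiro-Wilk, descriptive statistics, Kruskal-Wallis, Wilcoxon signed-rank, a paired t-test, Chi-squared and Fisher's exact test.

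No regression, ANCOVA, mixed model or stratified analysis is named, and age, gender and BMI are mentioned in no comparison.

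Two further passages bear on the point. The lay summary says when trainee data begin: "These outcome measures for the 'Trainee' group will commence following completion of the simulation training (if applicable"), so an StR has no earlier intra-operative motion value. Section 9.7 says how operations reach the StR: "The supervising Consultant will confirm the cases on the list" that the StR or Fellow will perform.

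**The concern.** Haemoglobin, EQ-5D and OHS have a pre-operative value that could serve as a covariate. Theatre time, path length, number of movements and length of stay do not. For these, age, sex and BMI are natural patient-level covariates, and they vary from one operation to the next within a registrar. Left out, whatever they explain stays in the error term of a comparison that has at most 8 registrars per arm.

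Case mix is a second issue. The StR is randomised; the patients are not. In the comparison of StRs with Experts and Fellows nothing is randomised, and the surgeon's grade is known when cases are shared out. If older or heavier patients tend to go to one grade, an unadjusted difference in operating time, motion totals or stay mixes patient differences with surgical experience. That comparison serves the secondary objectives of defining an expert standard and relating performance to experience.

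**Working it through.** **Inputs from the documents.** Up to 8 StRs per arm (sections 3 and 7; 12 to 16 in total in section 8.1); 8 patients per StR, 5 per Fellow, 5 per Consultant (section 3); age SD 11.4 years (section 5, registry figure).

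**The plan's own figure.** 16×8 + 8×5 + 5×5 = 128 + 40 + 25 = 193, as stated. This is a head count. There is no power calculation to reproduce, and no SD, ICC or effect size.

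**Assumptions.** ICC between registrars ρ = 0.05 to 0.30; share of within-registrar variance explained by age, sex and BMI R² = 0.05 to 0.20; two-sided 5% test; unadjusted power of 70% as the starting point.

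**Precision.** The registrar is the randomised unit, so the calculation uses registrar means. In units of total outcome variance, with m = 8 operations each:
- unadjusted: V₀ = ρ + (1−ρ)/8
- adjusted: V₁ = ρ + (1−ρ)(1−R²)/8
- reduction = 1 − V₁/V₀; equivalent extra registrars per arm = 8·V₀/V₁ − 8.

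Largest gain (ρ 0.05, R² 0.20): V₀ = 0.16875, V₁ = 0.14500, reduction 14.1%, equal to 1.31 registrars per arm.

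Smallest gain (ρ 0.30, R² 0.05): V₀ = 0.38750, V₁ = 0.38312, reduction 1.1%, equal to 0.09 registrars per arm.

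| ρ | R² 0.05 | R² 0.10 | R² 0.20 |
|---|---|---|---|
| 0.05 | 3.5% | 7.0% | 14.1% |
| 0.10 | 2.6% | 5.3% | 10.6% |
| 0.20 | 1.7% | 3.3% | 6.7% |
| 0.30 | 1.1% | 2.3% | 4.5% |

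**Power.** With 8 v 8 registrars (14 df), 70% power needs a noncentrality of 2.67. Dividing by √(V₁/V₀) gives 2.69 to 2.88, which is power of 70.5% to 76.4%. With 6 v 6 registrars the variance reductions are the same and the power range is again 70.5% to 76.4%.

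**Chance imbalance.** Treating patients as independent, the SE of the difference in mean age, 64 v 64, is 11.4×√(2/64) = 2.02 years. The 5% bound is 1.96×2.015 = 3.95 years, or 0.35 SD. Gaps of this kind are part of the sampling variation that the test already allows for. With no systematic shift, simulation of raw registrar means (ρ 0.1, R² 0.1) rejected 5.0% of the time.

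**A systematic shift, as a scenario only.** If the arms differed by s SD on a covariate with share R², the noncentrality under no training effect would be s·√(R²(1−ρ)) / √((2/8)·V₀). For s = 0.5 and R² 0.10 to 0.20, the false-positive rate is 9.3 to 13.8% at ρ 0.1 and 6.8 to 8.7% at ρ 0.30. For s = 0.25 at ρ 0.1 it is 6.1 to 7.1%. A 0.5 SD gap is 5.7 years of age, and 5.7/2.015 = 2.83 standard errors. Chance alone produces that about 0.5% of the time.

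**The case against.** Four arguments weigh against the point.

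1. **The gain is small and rests on assumed inputs.** This stands. Patient covariates cannot remove true differences between registrars. At ρ 0.20 and R² 0.10 the gain is 3.3%, or 0.28 of a registrar per arm. That sets the grade of the point but does not cancel it, because the data are already collected.

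2. **Case selection by arm is guarded against.** This largely stands. A reader might infer that, because the Consultant confirms cases after the StR is randomised, the arms will receive different patients. But section 9.7 says that neither the StR nor the investigator will disclose the arm, and section 9.5 says that assessors are blinded. Section 8.2 limits entry to primary osteoarthritis without complex pathology or previous surgery on that hip, and section 9.4 aims for an even split of the arms across sites. Selection by arm remains possible, for example if trained skill shows, but the documents do not show it. None of these safeguards balances patients between StRs and Experts or Fellows.

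3. **An inflated false-positive rate is not established.** This stands. A rate of roughly 10 to 15% could be read into the scenario above, but it needs a 0.5 SD systematic shift and an ICC near 0.1.

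4. **Other covariates may be better.** This stands in part. Section 11 has a blinded pre-operative X-ray grade of bone loss, and sections 9.2 and 9.6 give each StR a baseline written test and simulated procedure. Neither is used to adjust a comparison, and nothing in the documents ranks age, sex and BMI above them. The simulated procedure is not an operation, so it does not supply a pre-training intra-operative value.

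**Conclusion.** The point holds as a modest, low-cost improvement. Section 12 collects three patient variables that section 11 never uses, and the outcomes concerned have no pre-operative value. For intervention against control StRs the loss is one of precision: about 1 to 14% of the variance of the arm difference, 0.1 to 1.3 registrars per arm, or 70% power against 70.5 to 76%. The range depends wholly on the assumed ICC and R².

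Two stronger readings are not supported. The randomised comparison is not shown to be biased by case mix. Nor is the gain as large as it would look if patients were treated as independent, where the variance would fall by the full R² of 5 to 20%.

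For StRs against Experts and Fellows the case is stronger in kind, because nothing balances the patients. The documents give no basis for its size. Adjusting for three variables would reduce that confounding only as far as those variables capture it.

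**What to change.** In section 11, for theatre time, each motion metric and length of stay (log scale where skewed), pre-specify a linear mixed model with group, patient age, sex and BMI as fixed effects and a random effect for surgeon. Use small-sample degrees of freedom, such as Satterthwaite or Kenward-Roger, because there are only 12 to 16 randomised surgeons. Fit it once for intervention against control StRs and separately for StRs against Experts and Fellows. Report the unadjusted result beside each.

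Group must be in the same model as the covariates. Regressing on age, sex and BMI alone and then comparing mean residuals is not the same analysis. If the groups differ by 0.5 SD on a covariate (0.25 SD either side of the overall mean, within-group variance 1), a true effect of 0.50 is pulled to about 0.50 × 1/(1 + 0.25²) = 0.47.

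The cost is a paragraph of analysis text, a little more analysis work, and a model assumption in place of a rank test. No extra data, visits or patients are needed, and three covariates are easily supported by about 128 StR operations. Fixing the covariates before results are seen also prevents selective adjustment later.

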9.2. Informed Consent

The PI ([name]), or a suitably qualified deputy, will take informed consent from every participant involved in this study. This will be taken at their visit before any study specific procedures are performed.

Each participant must personally sign and date the latest approved version of the Informed Consent form at this visit. Written and verbal versions of the PIS and Informed Consent form (ICF) will be presented to the participants detailing no less than: the exact nature of the study; what it will involve for the participant; the implications and constraints of the protocol; and any risks involved in taking part. It will be clearly stated that the participant is free to withdraw from the study at any time for any reason, and with no obligation to give the reason for withdrawal. The participant will be allowed as much time as wished to consider the information, and the opportunity to question the Investigator, or other independent parties in order to decide whether they will participate in the study. Written Informed Consent will then be obtained by means of participant dated signature and dated signature of the person who presented and obtained the Informed Consent. A copy of the signed Informed Consent will be offered to the participant. The original signed form will be retained by the PI ([name]) at the study site

Visit 1 - Group 1 ('StR's):

Following enrolment for participation in this study, the StR's will be randomly allocated to receive either routine normal Deanery training (the 'control' group), or routine normal Deanery training plus additional simulation training (the 'intervention' group). Following randomisation all StR participants will undergo a baseline written and practical skills assessment within the OOSEC.

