9.3. Subsequent Visits

Group 1a ('StR's') - Intervention group:

StR's randomised to the 'intervention group' will be required to complete the 4-week period of additional training outlined in section 9.3. Following completion of this additional training, participants within this group will undertake approximately 2 intra-operative assessments every 6 weeks over the duration of their 6-month clinical placements (total 8 assessments). The StR's will also undertake a final Technical Skills assessment in OOSEC Laboratory at 3 months into their placement (See Appendix A for Study Flow Diagram).

Group 1b ('StR's') – control group:

Participants within this group will undertake approximately 2 intra-operative assessments every 6 weeks over the duration of their 6-month clinical placements (total 8 assessments). The StR's will also undertake a final Technical Skills assessment in OOSEC Laboratory at 3 months into their placement (See Appendix A for Study Flow Diagram).

Group 2: 'Experts' and 'Fellows':

Following enrolment for participation in this study, all participants within this group will undergo a baseline practical skills assessment within the OOSEC. Participants within this group will then undertake a minimum of 5 separate intra-operative assessments each.

Patients:

Following enrolment for participation in this study, all patients will be asked to complete the pre-operative PROMs questionnaires (EQ-5D and OHS). These are part of routine clinical care, and are a mandatory for all patients undergoing THR in the NHS. The patients will not be asked to undertake any further assessments outside of their routine clinical care until the time of their scheduled post-operative out-patient department (OPD) clinic review appointment. All patients will only be followed up routinely following discharge by their named Consultant in an OPD clinic. This OPD appointment normally takes place 6 to 8 weeks following discharge. No additional clinic appointments or investigations will be required outside of the patients expected routine clinical care. At this visit the patients will be asked to complete the post-operative validated PROMs questionnaires (EQ-5D and OHS). This takes a few minutes and is the only extra outcome measure the patients are asked to complete.

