9.5 Blinding and code-breaking

Standard surgical practise will be followed. Patients are not formally blinded to which Surgeon (Consultant, Fellow, or StR) performs their operation, and are informed if requested. In line with standard surgical practise and training within the NHS, patients will provide informed consent that they understand no guarantees can be given that a particular person will perform the procedure. The person will, however, have appropriate experience.

Due to the nature of this study the StR's cannot be blinded to their allocations into either the 'control' or 'intervention' groups, however the assessment methods and any assessors will be blinded.

9.6 Description of study intervention(s),

The intervention to be tested is the simulation-based and cognitive learning package, which will be delivered to a randomised sub-group of 50% of the StR's recruited into this study. This will be delivered in a supervised setting within the OOSEC over a 4-week period for between 1 to 2 hours per week, over 3 to 4 consecutive but separate six-month placements (please see Appendix A for Study Flow Diagram). This will take place on a Wednesday afternoon, which is when all the Regional StR's are due to attend teaching in Oxford at the NOC.

The OOSEC is a secure enclosed laboratory space within the NOC, which contains all the necessary equipment required to run the simulation-based and cognitive learning training. The simulation training in general may include:

- 1) Focussed workshops on saw-bone models (simulated bones)
- 2) Digital and computer-based cognitive learning packages
- 3) Virtual reality platforms.

All participants within group 1 (StR's) will be asked to attend and complete baseline and final assessments within the OOSEC, which will consist of a multiple-choice questionnaire (MCQ) and a simulated procedure. Participants within group 2 (Consultants and Fellows) will only be required to complete a baseline simulated procedure.

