12.4 Source Data

Please see section 12 on Data management for further details. In general, the source data is as follows:

Intra-Operative Data

- Wireless motion data.
- Global rating scales and checklists.

Hospital Records Data

- NHS EPR for laboratory and clinical data.

- Insignia PACS for radiograph (x-ray) analysis.
- TMS for theatre lists, workflow, and productivity information.

Questionnaire Data

- PROMs questionnaire forms to be completed pre- and post-op (as detailed above).
- Participant performance assessment tools and feedback forms.

All confidential data will be stored securely. On all study-specific documents, other than the signed consent, the participant and patients will be referred to by the study UPI, and not by name.

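### Section 11 compares the registrar arms on OHS, EQ-5D and haemoglobin without using the pre-operative values it collects, leaves the analysed form of the PROMs open, names a paired test for independent arms, and plans before/after-training comparisons with no 'before' data

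*Combined protocol and SAP*

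**What the plan says.** **Collection.** Section 9.3 states that "all patients will be asked to complete the pre-operative PROMs questionnaires (EQ-5D and OHS", and the same questionnaires are repeated at the routine out-patient review. Section 12.4 confirms this: "PROMs questionnaire forms to be completed pre- and post-op (as detailed above". Appendix B schedules blood tests at the pre-operative clinic and again during the in-patient stay.

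**Analysis.** Section 11 (Other outcomes data) gives a general rule: "Statistical analyses between each group of participants will be performed using either the parametric unpaired t-test or a non-parametric Mann-Whitney U test", according to distribution. For the registrars it adds that analysis "using a paired t-test, or Mann-Whitney U test will also be performed within the two sub-groups of the StR's (control and intervention". The same sentence ends by planning a further comparison, this one "within the intervention sub-group in order to compare outcomes before and after additional training". The PROMs are listed by instrument name only. Haemoglobin appears as "Blood loss (pre-/post-op haemoglobin levels". Across section 11 the named tests are Shapiro-Wilk, t-tests, Mann-Whitney, Kruskal-Wallis, Wilcoxon signed-rank, chi-squared and Fisher's exact. There is no regression model, no covariate and no term for the operating surgeon.

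**Trainee baseline.** Section 9.2: "Following randomisation all StR participants will undergo a baseline written and practical skills assessment within the OOSEC". Section 9.5: "Due to the nature of this study the StR's cannot be blinded to their allocations", although assessors are said to be blinded.

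**The concern.** PROMs and blood loss sit under the primary objective (section 6), and only 6 to 8 registrars per arm are expected (section 9.4). Four things follow from the text.

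- Baselines that are already collected are not used to sharpen the arm comparison.
- For OHS and EQ-5D the analysed quantity is open. Post-operative value and change differ in precision, in a direction that depends on the pre/post correlation, and an open choice can be made after results are seen.
- The test named for the registrar arms is partly the wrong one. The arms hold different surgeons and different patients, so nothing pairs across them.
- The before/after-training comparisons in the intervention arm need operative and patient data from before training, and the protocol does not appear to collect any.

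**Working it through.** **Inputs from the protocol.** 8 registrars per arm (sections 3 and 7), possibly 6 (section 9.4); 8 patients per registrar (section 3). The plan's only sample-size figure is a count, and it reproduces: 16 × 8 + 8 × 5 + 5 × 5 = 128 + 40 + 25 = 193. No alpha, power, SD, correlation or ICC is stated.

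**Assumptions.** Two-sided 5%, 80% power; ICC 0.05 (0 and 0.10 as a range); pre/post correlation r of 0.3, 0.5 or 0.7 acting within surgeon; equal pre- and post-operative SDs.

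**Precision.** For k registrars per arm with 8 patients each, in units of the outcome SD,

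variance of the arm difference = (2/k) × [ICC + (1 − ICC) × f/8],

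with f = 1 for the post-operative value, 2(1 − r) for change and 1 − r² for ANCOVA. The detectable difference uses the noncentral t with 2k − 2 degrees of freedom.

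Worked case, k = 8, ICC 0.05:

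- Post-operative value: 0.25 × (0.05 + 0.95/8) = 0.25 × 0.16875 = 0.0422; standard error 0.205; detectable difference 0.62 SD.
- ANCOVA at r = 0.5: 0.25 × (0.05 + 0.95 × 0.75/8) = 0.25 × 0.1391 = 0.0348; detectable difference 0.56 SD. Variance falls by 1 − 0.0348/0.0422 = 18%.

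| Detectable difference (SD), ICC 0.05 | r = 0.3 | r = 0.5 | r = 0.7 |
|---|---|---|---|
| 8 per arm, post-operative value | 0.62 | 0.62 | 0.62 |
| 8 per arm, change | 0.70 | 0.62 | 0.53 |
| 8 per arm, ANCOVA | 0.60 | 0.56 | 0.50 |
| 6 per arm, post-operative value | 0.74 | 0.74 | 0.74 |
| 6 per arm, change | 0.84 | 0.74 | 0.63 |
| 6 per arm, ANCOVA | 0.71 | 0.67 | 0.60 |

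The variance reduction from ANCOVA at ICC 0, 0.05 and 0.10 is 9%, 6% and 5% (r = 0.3); 25%, 18% and 13% (r = 0.5); 49%, 35% and 26% (r = 0.7). If r also acted between surgeons, ANCOVA with 8 per arm at ICC 0.05 would reach 0.59, 0.54 and 0.44 SD, so the table is the more cautious version.

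Change is worse than the post-operative value below r = 0.5 and better above it. Apart from about one degree of freedom, ANCOVA is no worse than either.

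**Clustering.** Registrars are randomised, but the named t-test treats 64 patients per arm as independent. The true variance is larger by 1 + 7 × ICC, that is 1.35 at ICC 0.05 and 1.70 at ICC 0.10. The approximate type I error is 2 × P(Z > 1.96/√1.35) = 9.2% and 2 × P(Z > 1.96/√1.70) = 13.3%. Simulation of the patient-level t-test (40,000 runs per setting, 8 v 8 and 6 v 6) agrees: about 5% at ICC 0, 9% at 0.05 and 13% at 0.10.

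**Before and after training.** Section 11 plans such comparisons in the intervention arm for motion metrics, X-ray grade, cup position and patient outcomes. The lay summary starts all trainee outcome measures once training is complete, and section 9.3 places the intervention arm's operative assessments after it. The laboratory baseline could supply a 'before' score for simulated performance only; it cannot supply an X-ray, a cup angle or a patient outcome.

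**The case against.** The strongest reply is that unadjusted comparisons are legitimate in a randomised study, so nothing worse than some lost precision is at issue. Lack of adjustment alone does not invalidate a test, and that part stands. It does not rescue the tests as written: they ignore clustering within registrar, and the error rates above show the cost. A reader should not infer that the planned tests are sound apart from precision.

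The gain from ANCOVA is modest and rests on assumed values. This also stands. At r = 0.3 the detectable difference moves only from 0.62 to 0.60 SD, and the documents give no r that would favour a larger figure. The detectable differences describe a clustered analysis that section 11 does not contain, so they show what adjustment adds to a sound model and do not measure the current plan.

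Haemoglobin is not wholly undefined: listing pre- and post-operative levels under blood loss most naturally means the drop. That is accepted; the open form concerns OHS and EQ-5D.

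The paired t-test might be meant within each arm, before against after surgery. The sentence does not say so, and the only before/after contrast it names is training. Such a comparison would show change after hip replacement, and would not compare the arms.

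Finally, a reader might infer that a laboratory baseline taken after unblinded allocation biases the trial. The documents do not support this. No planned between-arm test uses that score, and when trainees learn their arm is not stated. The flow chart in Appendix A is not available to check.

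**Conclusion.** The point holds as an improvement that should be made. For OHS, EQ-5D and haemoglobin the plan collects the baseline and names no analysis that adjusts for it; for the two PROMs it does not fix what is analysed; and the paired t-test does not fit independent arms. Adjusting lowers the detectable difference from 0.62 SD to between 0.60 and 0.50 SD for 8 registrars per arm, given ICC 0.05 and r from 0.3 to 0.7, all assumed.

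The benefit does not reach motion metrics, rating scales, cup position, theatre time, length of stay, transfusion or morbidity, which have no matching pre-operative value. It would be too strong to say that the primary objective as a whole loses precision for this reason.

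Two conclusions do not depend on r. Any test of these outcomes, adjusted or not, must account for clustering. And the before/after-training comparisons conflict with the lay summary and section 9.3. The order of the laboratory baseline is a minor matter of good practice.

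**What to change.** 1. In section 11, compare the registrar arms on post-operative OHS, EQ-5D and haemoglobin by ANCOVA on the matching pre-operative value, in a model that accounts for patients clustered within registrar, with small-sample degrees of freedom. This replaces the paired t-test. If the haemoglobin drop is preferred for reporting, adjusting it for the pre-operative level gives the same arm difference.
2. Any unadjusted sensitivity analysis should state the analysed form and also account for clustering.
3. Give a rule for patients with a missing pre-operative value.
4. For each before/after-training comparison, state the source of the 'before' value, and remove those that have none.
5. Minor: in section 9.2, complete the laboratory baseline before the allocation envelope is opened.

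Settle items 1 to 4 before outcome data are examined by arm. The cost is rewording section 11 and reordering two steps of the first visit, with no new data. The downsides are about one degree of freedom per covariate and the missing-baseline rule.
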